## 5. Study Design

### 5.1. Overall Design

This is a randomized, controlled study for treatment of mild COVID-19 in people at high risk for disease progression.

Mild COVID-19 is determined by Gates MRI mild COVID-19 clinical endpoint definition (refer to [Table 7](#)).

High risk is defined based on age, BMI or presence of a comorbidity.

**Primary purpose:** To assess the safety and clinical efficacy of rivaroxaban in reducing the proportion of participants who have progressed to moderate or severe disease category or higher in people with mild COVID-19 who are at increased risk of disease progression.

**Interventional model:** Participants will be randomized 1:1 to either the rivaroxaban or the placebo group, in parallel for the duration of the study. Randomization will be stratified by site and by number of days since onset of symptoms (<6 days vs.  $\geq 6$  days).

#### **Intervention groups:**

- Study intervention group: Rivaroxaban, 10 mg (1 tablet) orally daily for 21 days.
- Control group: placebo-equivalent (multi-vitamin supplement) 1 tablet orally daily for 21 days.

**Masking:** Every effort will be made to mask the assigned treatment groups. Participants and study staff evaluating them will not be told of the assigned treatment groups. The laboratories performing the SARS-CoV-2 diagnostic testing will be blinded. Refer to [Section 6.7](#) for details.

**Study visits:** Every effort will be made to conduct the study protocol visits virtually (defined in [Section 8](#)) with the study participants. A web-based video conferencing tool will be employed to allow for virtual (remote) interactions to take place between the study staff and the participant, for screening and all study visits.

**Safety and efficacy monitoring:** Refer to [Section 6.5](#) for safety monitoring. An IDMC will be convened for this study for safety and efficacy with expertise in COVID-19 or respiratory viruses and emerging epidemics as well as biostatistics. Refer to [Section 11.1](#) for details regarding the IDMC.

### 5.2. Study Population

The total number of participants enrolled will be approximately 600, with 300 participants per group.

Refer to [Section 5.5.1](#) for eligibility criteria.

### 5.3. Recruitment

Study screening processes will occur for participants at high risk for severe COVID-19 who are mildly symptomatic and have or suspected to have COVID-19 (refer to [Section 5.4](#) for pre-screening and to [Section 5.5](#) for screening). There is an opportunity for high risk participants

with COVID-19 who are currently asymptomatic to be pre-screened for this study; however, pre-screening is not a pre-requisite to entering the study.

#### 5.4. Pre-Screening for the Study

[figure not shown]
The purpose of pre-screening is to facilitate enrollment of participants with mild COVID-19 into the study as soon as they become symptomatic. Persons who are in the high risk category for COVID-19 progression and are asymptomatic may enroll in the pre-screening phase provided that they are willing to be contacted by the study team and are interested in enrolling in the COVID-19 treatment trial if they become symptomatic. They must have a confirmed positive SARS-CoV-2 diagnostic testing within the past 7 days at Day 1 of pre-screening.

Participants who do not yet have a documented positive SARS-CoV-2 diagnostic test may have the testing done at the pre-screening eligibility check visit provided that they have had a high risk **exposure** to SARS-CoV-2 within the past 14 days.

High risk exposure is defined as:

1. being an immediate household contact of a confirmed COVID-19 case and/or
2. having occupational exposure to a confirmed COVID-19 case (for example, healthcare worker or first responder).

**Figure 2: Pre-Screening for the Study**

### **5.4.1. Pre-Screening Inclusion Criteria**

#### **Age**

1.  $\geq 18$  years of age at the time of informed consent

#### **Type of Participant**

2. Participants must be at high-risk for COVID-19 progression by fulfilling at least **one** of the following criteria at screening:
  - Age  $\geq 65$  years
  - Presence of a chronic disease requiring daily treatment (such as diabetes, lung disease, heart disease, hypertension or cancer)
  - Self-reported obesity
  - Any other high-risk criteria per national guidelines.

#### **COVID-19 characteristics**

3. Documented positive SARS-CoV-2 diagnostic testing with sample collected  $\leq 7$  days at Day 1 of pre-screening
4. No COVID-19 symptoms (defined as fever, chills, myalgia, arthralgia, headache, fatigue, cough, sore throat, nasal congestion, anosmia, ageusia, nausea, vomiting, or diarrhea, that are either new onset or have worsened from baseline\*).

\*Baseline refers to health status prior to contracting COVID-19.

#### **Informed Consent**

5. Capable of giving informed consent, which includes compliance with the requirements and restrictions listed in the Pre-screening informed consent form (ICF)

#### **Sex**

6. Male or female

#### **Others**

7. Willing to be contacted by study team and to notify study team if any COVID-19 symptom occurs
8. Interested in participating in a treatment trial if symptoms of COVID-19 occur.

#### 5.4.2. Pre-Screening Procedures

The pre-screening Schedule of Activities is shown in [Table 4](#).

**Table 4: Pre-screening Schedule of Activities**

Pre-screening Visits 	Eligibility check (≤72 hrs)	Pre-screening (Day 1 to Pre-screening Day 10)
Obtain informed consent	X	
Eligibility criteria	X	
SARS-CoV-2 diagnostic testing 	X	
Daily contact with study team to check if symptomatic for COVID-19 		X
No AEs will be collected		

If documented positive SARS-CoV-2 testing is not available at the eligibility check visit, testing may be performed provided that the potential participant has had a high risk exposure to SARS-CoV-2, defined as being an immediate household contact of a confirmed COVID-19 case and/or having occupational exposure to a confirmed COVID-19 case (for example, healthcare worker or first responder).

Participant will exit the pre-screening phase if he/she remains asymptomatic at day 10 after diagnosis or day 10 of the pre-screening phase, whichever comes first.

After the pre-screening ICF is signed and eligibility is confirmed, participants are asked to notify the study staff immediately if any COVID-19 symptom occurs. Study staff will also contact participants daily by phone or text or electronically to inquire about symptoms. If a participant does not have any COVID-19 symptoms at day 10 from SARS-CoV-2 diagnosis or day 10 of the pre-screening follow-up, the participant will be asked to exit the pre-screening phase.

Note that no data during the pre-screening stage will be recorded in the database or in a case report form.

## 5.5. Screening for the Study

Refer to [Section 8.1](#) for screening procedures.

### 5.5.1. Inclusion and Exclusion Criteria

Participants are eligible to be included in the study only if all of the following criteria apply:

#### Age

1.  $\geq 18$  years of age at the time of informed consent

#### Type of Participant

2. Participants must be at high-risk for COVID-19 progression by fulfilling at least **one** of the following criteria at screening:

- Age  $\geq 65$  years
- Presence of chronic pulmonary disease, chronic obstructive pulmonary disease (COPD), pulmonary hypertension
- Diabetes mellitus (type 1 or type 2), requiring oral medication or insulin for treatment
- Hypertension, requiring at least one oral medication for treatment
- Immunocompromised status due to disease (e.g., those living with human immunodeficiency virus with a CD4 T-cell count of  $<200/\text{mm}^3$ )
- Immunocompromised status due to medication (e.g., taking 20 mg or more of prednisone equivalents a day, anti-inflammatory monoclonal antibody therapies, cancer therapies)
- Any chronic disease that is associated with high risk for severe COVID disease in the opinion of the site investigator
- Body mass index  $\geq 35 \text{ kg/m}^2$  (based on self-reported weight and height).

#### COVID-19 Characteristics

3. Documented positive SARS-CoV-2 diagnostic testing with a sample collected  $\leq 10$  days of screening.
4. Symptomatic for COVID-19 for  $\leq 7$  days at time of randomization (symptomatic is defined as having at least one of the following symptoms of COVID-19 that is of new onset or has worsened from baseline: fever, chills, myalgia, arthralgia, headache, fatigue, cough, sore throat, nasal congestion, nausea, vomiting, or diarrhea).

#### Informed Consent

5. Capable of giving informed consent, which includes compliance with the requirements and restrictions listed in the ICF and in this protocol

#### Sex

6. Male or female

## **Other Requirements:**

7. Agree to participate in all remote, in-person or home visits as required in the protocol and provide updated contact information as necessary.
8. Female of childbearing potential must agree to practice adequate contraception during the study ([Section 9.8.1](#)).

### **5.5.2. Exclusion Criteria**

Participants are excluded from the study if any of the following criteria apply:

#### **Medical Conditions or history**

1. Currently hospitalized or under immediate consideration for hospitalization at screening and Day 1
2. Have new onset shortness of breath or increased shortness of breath from pre-COVID-19 (for people with known COPD) at screening and Day 1
3. Hypoxemia (oxygen saturation<94% in ambient air or oxygen saturation below pre-COVID-19 oxygen saturation [if known] for people with known COPD) at Day 1
4. Require supplemental oxygen (new requirement or increase in requirement from pre-COVID-19 condition) at screening and Day 1
5. Have a history of (in the past 3 months) or current active pathological bleeding
6. Have a history of hemorrhagic stroke or intracranial hemorrhage
7. Have a recent severe head trauma within 30 days which includes concussion, skull fracture or hospitalization for head injury
8. Have known intracranial neoplasm, cerebral metastases, arteriovenous malformation or aneurysm
9. Have history of pregnancy-related hemorrhage
10. Have active gastroduodenal ulcer or other gastrointestinal bleeding diagnosed in the past 3 months
11. Currently are in a hemodynamically unstable state
12. Currently require thrombolysis or pulmonary embolectomy
13. Have history of severe hypersensitivity reaction to Xarelto®
14. Currently have a prosthetic heart valve
15. Have known diagnosis of triple positive antiphospholipid syndrome
16. Have known diagnosis of chronic kidney disease (stage IV or receiving dialysis)
17. Have a history of thrombocytopenia or known platelet count < 100,000 cells/mm^3
18. Have a history of bronchiectasis and pulmonary cavitation
19. Have active cancer (eg, receiving chemotherapy or treatment for complication of the active cancer)

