### **3.2. Rivaroxaban**

Xarelto® (rivaroxaban) is manufactured by Janssen Pharmaceutical Companies of Johnson & Johnson and was first approved by the FDA in 2011. Xarelto® is currently approved for the following indications [Xarelto® 2020]:

- reduce risk of stroke and systemic embolism in nonvalvular atrial fibrillation (15 or 20mg daily)
- treatment of DVT (20mg daily after initial treatment of 15mg twice daily for 21 days)

- treatment of PE (20mg daily after initial treatment of 15mg twice daily for 21 days)
- reduce risk of recurrence of DVT or PE (10mg daily after at least 6 months of standard anticoagulation treatment)
- prophylaxis of DVT, which may lead to PE in patients undergoing knee or hip replacement surgery (10mg once daily)
- prophylaxis of VTE in acutely ill medical patients (10mg once daily during hospitalization and 31-39 days after hospital discharge)
- reduce risk of major cardiovascular events in patients with chronic coronary artery disease or peripheral artery disease (2.5mg twice daily in combination with daily aspirin).

During clinical development for these approved indications, Xarelto® was evaluated in approximately 30,000 patients. The contraindications for Xarelto are active pathological bleeding and severe hypersensitivity reaction to Xarelto®. They will be followed as AESIs in this study.

The use of rivaroxaban for mild COVID-19 will follow usage guidelines for the prophylaxis of VTE in acutely ill medical patients who are at risk for thromboembolic complications due to moderate or severe restricted mobility and other risk factors for VTE and not at high risk of bleeding. The recommended dosage for this use is 10mg once daily, in hospital and after hospital discharge, for a total recommended duration of 31 to 39 days. The dosing in this study of 10mg daily for 21 days is in line with the indicated dose. Renal considerations for dosage include  $\text{CrCl} \geq 15 \text{ mL/min}$ . This study will exclude people with severe chronic kidney disease (stage IV or receiving dialysis).

According to the package insert, Xarelto® increases the risk of bleeding, and, although rare, can cause serious or fatal bleeding. Concomitant use of other drugs that impair hemostasis increases the risk of bleeding. Xarelto® is not for use for primary VTE prophylaxis in these hospitalized, acutely ill medical patients at high risk of bleeding.

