#### **3.2.3.1. Benefit/Risk Assessment of Rivaroxaban**

Without any approved treatment for outpatients with COVID-19, there is a favorable benefit-risk ratio for using rivaroxaban in the target population at increased risk for progressing to moderate and severe COVID-19.

Rivaroxaban is an approved drug with a well-characterized and favorable safety profile.

The dose selected for this study (10mg/day) is the same as the licensed prophylactic dose for VTE in acutely ill patients and fits the purpose of preventing thromboembolic events in people with acute COVID-19 illness. This study will exclude people who may be at increased risk for adverse events or drug interactions due to rivaroxaban as well as those with severe renal and liver impairment, and pregnant and breastfeeding women.

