#### ***Excretion***

In a Phase 1 study, following the administration of [C]-rivaroxaban, approximately one third (36%) was recovered as unchanged drug in the urine and 7% was recovered as unchanged drug in feces. Unchanged drug is excreted into urine, mainly via active tubular secretion and to a lesser extent via glomerular filtration (approximate 5:1 ratio). Rivaroxaban is a substrate of the efflux transporter proteins, P-glycoprotein (P-gp) and ABCG2 (also abbreviated Bcrp). Rivaroxaban's affinity for influx transporter proteins is unknown.

Rivaroxaban is a low-clearance drug, with a systemic clearance of approximately 10 L/hr in healthy volunteers following intravenous administration. The terminal elimination half-life of rivaroxaban is 5 to 9 hours in healthy subjects aged 20 to 45 years, and 11 to 13 hours in the elder participants aged 60 to 76 years

Pharmacokinetics (PK) and pharmacodynamics (PD) of rivaroxaban were not influenced by gender, but by race (higher exposure in healthy Japanese) and severe renal and liver impairment (which are exclusion criteria in this study). Please refer to package insert for more information.

Refer to [Section 6.4](#) for dose modification and toxicity management.

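### The protocol says severe renal and liver impairment are excluded, but the exclusion list does not name stage V kidney disease without dialysis and has no liver criterion

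*Protocol*

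**What the plan says.** Four places in the protocol bear on this.

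- **Section 3.2.3.1 (benefit/risk)** says the study will leave out people at increased risk from the drug, "as well as those with severe renal and liver impairment, and pregnant and breastfeeding women". It gives no stage or other limit.
- **Section 3.2.5 (pharmacokinetics, under Excretion)** says exposure and effect are influenced by "severe renal and liver impairment (which are exclusion criteria in this study").
- **Section 3.2 (background)** says "This study will exclude people with severe chronic kidney disease (stage IV or receiving dialysis"). The sentence before it, beginning "Renal considerations for dosage include", gives a creatinine clearance of at least 15 mL/min.
- **Section 5.5.2, criterion 16,** is the operative rule: "Have known diagnosis of chronic kidney disease (stage IV or receiving dialysis").

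The exclusion list opens with "Participants are excluded from the study if any of the following criteria apply", so a person is excluded only when a listed criterion is met. The SAP does not address renal or liver eligibility.

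**The concern.** Two narrative sections describe an exclusion that is wider than the list sites were told to apply. For the kidney, the list stops at stage IV and dialysis, without adding higher stages. For the liver, it says nothing.

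The protocol gives its own reasons why this matters. Section 3.2.5 reports 36% of the drug recovered unchanged in urine and says that severe renal and liver impairment influence its pharmacokinetics and pharmacodynamics. Section 3.2 says the drug raises the risk of bleeding, rarely serious or fatal. Section 6.4 allows no dose modification. A person who fell through the gap and was randomised to rivaroxaban would be someone Section 3.2.3.1 says was kept out.

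There is also a reporting risk. If the clinical study report repeats the wording of Sections 3.2.3.1 or 3.2.5, it would claim exclusions that the criteria did not impose.

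**Working it through.** No arithmetic applies. The check is to read the list literally, look for any other rule that closes the gap, and compare the result with the narrative.

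**1. The statements side by side**

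| Condition | Sections 3.2.3.1 and 3.2.5 | Section 3.2 | Section 5.5.2 |
|---|---|---|---|
| Kidney disease, stage IV | Excluded as severe | Excluded | Excluded (criterion 16) |
| Kidney disease, on dialysis | Excluded as severe | Excluded | Excluded (criterion 16) |
| Kidney disease, stage V, no dialysis | Excluded as severe, if stage V is worse than stage IV | Not named | Not named |
| Severe liver impairment | Excluded | No exclusion stated | No criterion |

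**2. Does another eligibility rule catch these people?** None of the other 25 exclusion criteria concerns kidney or liver function. Some people with severe liver disease might be excluded for another reason, such as thrombocytopenia or recent bleeding, but not for the liver condition itself. There is no general exclusion at the investigator's judgement. The creatinine clearance figure in Section 3.2 is not carried into eligibility. Inclusion criterion 2 in Section 5.5.1 accepts any chronic disease that the site investigator regards as carrying a high risk of severe COVID-19, so advanced kidney or liver disease could itself be the qualifying condition.

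**3. Would a test reveal them?** The Schedule of Activities (Table 1) has no creatinine, liver or other blood test. Section 8.1 relies on medical history, and criterion 16 requires a known diagnosis. Criterion 16 is therefore the only renal eligibility safeguard, and there is none for the liver.

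**4. What protects participants after enrolment?** Section 7.1 stops study drug for a contraindication to it. Section 7.2 allows withdrawal at the request of the primary care provider or at the discretion of the investigator or sponsor. Sections 6.4, 9.2 and 9.3 provide for bleeding checks at follow-up visits. These reduce the gap but do not close it, because they act after randomisation. The contraindications that Section 3.2 lists are active pathological bleeding and severe hypersensitivity, neither of which is renal or hepatic.

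**5. Would planned reporting show it?** Not reliably. A participant who meets the criteria as written is not an eligibility deviation, so the deviation summary in SAP 10.1 need not flag one. Neither kidney nor liver disease is a separate baseline category in SAP 10.2 or a subgroup in SAP 11.1.3 and 12.1. Medical history is coded and listed for the randomised population (SAP 13.1), so a targeted look is possible.

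**The case against.** The strongest reply is that the protocol explains its own term. Section 3.2 attaches the stage IV or dialysis bracket to the word severe, and criterion 16 repeats the bracket. Sections 3.2.3.1 and 3.2.5 can then be read as shorthand for that definition, and the kidney statements agree. They conflict only if a staging scheme is brought in from outside, and stage V appears nowhere in the documents. The aim was plainly stage IV and beyond, and sites may well have excluded stage V as a matter of course.

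Most of this stands as an account of intent, and it makes a drafting omission the likeliest explanation. A reader might infer that the protocol chose to admit stage V disease, or that such people were enrolled. The documents support neither. But intent does not alter what the list says, and the assumption that stage V is worse than stage IV is the ordinary one.

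The reply does not help with the liver. Sections 3.2.3.1 and 3.2.5 name severe liver impairment as excluded, no section qualifies the term, and no criterion implements it. That mismatch needs no staging scheme.

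A further reply is that randomisation stopped on 4 February 2021 (SAP Section 4), so rewording changes nothing in this trial. That is correct for enrolment. It does not cover how the enrolled population is described.

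**Conclusion.** The exclusion list does not fully implement the exclusions stated in Sections 3.2.3.1 and 3.2.5. Stage V kidney disease without dialysis is not literally excluded, and severe liver impairment is not addressed at all. The kidney part rests on the assumption that stage V is more severe than stage IV. The liver part rests on the text alone.

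The size is modest:

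- The documents give no count. The number affected is unknown and probably very small.
- With 1:1 allocation, about half of any such participants would be expected to have received the multivitamin control. Only those randomised to rivaroxaban would have altered exposure to the anticoagulant.
- The sample size assumptions in Section 10.1 and the efficacy analyses do not depend on renal or liver status, so no efficacy result depends on this point.

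Two stronger readings should be resisted. One is that the favourable benefit/risk assessment fails. Section 3.2.3.1 rests it mainly on the lack of an approved outpatient treatment and on a well-characterised drug; the exclusions are one supporting sentence. The other is that participants had no protection, which overlooks the rules that apply after enrolment.

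**What to change.** 1. The sponsor should reconcile Sections 3.2, 3.2.3.1, 3.2.5 and 5.5.2 so that the renal and liver exclusions are stated consistently. Which limits are right is a clinical decision for the sponsor; none is proposed here.
2. Check recorded medical history for randomised participants with stage V kidney disease not on dialysis or with severe liver impairment. The check may be incomplete, because the documents do not say that kidney disease stage was recorded, and coded terms may not show it.
3. Report any found, with their arm and bleeding outcomes.
4. In the clinical study report, describe the exclusions as they were written. State that all severe renal and liver impairment was excluded only if the check confirms it.

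The cost is a wording correction, one query of data already collected, and a few lines in the report. If a later protocol in the same platform reuses these criteria, the corrected wording should go with them.

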**Other:**

20. Had epidural or neuraxial anesthesia or spinal puncture in the past 2 weeks or plan to undergo these procedures during the study
21. Had surgery in the past 4 weeks or plan to undergo surgery during the study
22. Currently is pregnant or plans to become pregnant (refer to [Section 9.8](#))
23. Currently is breastfeeding
24. Share household with an enrolled participant in this study
25. Co-enrollment in any clinical trial that includes prohibited procedures (spinal puncture or surgery) or that includes treatments within the same drug class as rivaroxaban or treatments for which co-administration with rivaroxaban are prohibited\*

\*Note that any co-enrollment other than this requires approval by the Sponsor. For any co-enrolled study, the total volume of blood samples collected across the studies should not exceed 275 mL in 4 weeks.

